4.2 Arm A: NEL with Temporising Device - (Intervention)

NEL with Temporising Device

Infants allocated to the NEL with temporising device arm (Arm A) will undergo insertion of an endoscope into the lateral ventricle via a peel-away catheter on the side of higher blood load. Ultrasound guidance may be used at the surgeon's discretion for optimal placement of the endoscope. Following irrigation of the lateral ventricle with Ringer's Lactate or other appropriate lavage solution, the third ventricle and contralateral ventricle (via a septostomy) are also irrigated until the effluent is clear. Blood clots on the ependymal surface may be gently aspirated. The endpoint of the lavage will be at the surgeon's discretion and defined as a 'maximal safe lavage' when the effluent is clear and there has been an attempt to dislodge and wash out clots. This endpoint has been clearly defined by a consensus process of the involved surgeons (28). Once the procedure is completed, a temporising device (either a VAD or VSGS) is inserted, at the discretion of the treating surgeon in line with local practice. Please refer to Table 6 for details of mitigations of risks associated with NEL.

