4.3 Arm B: Temporising Device Alone - (Control)

Temporising Device Alone

Infants allocated to the temporising device arm (Arm B) will undergo the standard surgical procedure to insert either a VAD or VSGS, at the discretion of the treating surgeon, in line with their standard current practice. Both VAD and VSGS are associated with the same operative and post-operative risk, namely infection, recurring haemorrhage inside the ventricles, new haemorrhage related to ventricular decompression, catheter blockage, failure of absorption of

CSF from the subgaleal pocket of a ventricular-subgaleal shunt, seizures, external leakage of CSF, electrolyte disturbance and a very small risk of stroke. In our experience, all these are rare and occur in less than 5% of cases. The management of these risks will remain at the discretion of the treating neurosurgical team.

4.4 **Concomitant Care**

Premature infants are at risk of multiple medical problems involving many organ systems. Therefore, any concomitant treatments needed by the infant during the study period are permitted. These infants are typically on multiple medications, and data on their administration is beyond the remit of this study. However, details of prescribed prophylactic antibiotics and anti-epileptic medications must be recorded as per section 3.6 (Trial Visits).

4.5 **Unblinding**

Due to the study design, only the primary outcome assessor and individuals making strategic decisions for the trial including the Trial Statistician and the Clinical Project Manager will be blinded to the treatment arm. Therefore, emergency unblinding is not necessary.

Protocol Treatment Discontinuation

In consenting to the trial, parent/legal guardian(s) of participants are consenting to the infant's trial procedure (either Arm A NEL with Temporising Device or Arm B Temporising Device alone), trial follow-up and data collection. However, an individual parent/legal guardian can request to stop trial follow-up and data collection early for any of the following reasons:

- 1. Any change in the participant's condition that in the clinician's opinion justifies the cancellation of planned trial surgery.
- Withdrawal of consent for participation in the trial by the parent/legal guardian(s)
 The participant never underwent standard of care insertion of a temporising device.

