5.1.2 Secondary Outcomes

The secondary outcome measures are:

- 1. Developmental Measures:
 - a. Motor quotient (MQ): Age equivalent motor score of the Bayley IV divided by corrected age at assessment, measured at 2 years' corrected age
 - b. Language quotient (LQ): Age equivalent language score of the Bayley IV divided by corrected age at assessment, measured at 2 years' corrected age
- 2. Other neurological and functional assessments conducted during the 2-year follow-up visit:
 - a. Presence of seizures during the first 2 years and use of anticonvulsant medication at 2 years.
 - Presence of cerebral palsy (+ accompanying Gross Motor Function Classification System (GMFCS) grade and deficit distribution map using the Classification of SCPE
 - c. Assessment of hearing and vision (British Association of Perinatal Medicine classification)
 - d. Parent report:
 - i. Brief Infant Toddler Social Emotional Assessment (BITSEA)
 - ii. Quantitative Checklist for Autism in Toddlers (Q-CHAT)
- 3. Mortality up to 2 years corrected age.
- 4. NEL & VP shunt related outcomes:

- a. Safety of NEL: Number of Adverse Events, where Adverse Events would include (and not limited to) secondary bleeding in the brain, post-operative infections, temporising device survival, mortality, stroke, seizures, electrolyte disturbances, CSF leak, unexpected readmissions or return to theatre.
- b. Number and type of further surgical procedures, including revision of the temporising drainage device (VAD or VSG), addition of a second temporising device, surgery for loculated or isolated ventricles, and revisions of the VP shunt, if implanted, until two years' corrected age. These infants often need multiple shunt revisions during their first two years of life. We will have a separate CRF to record data related to these unexpected presentations and procedures.
- c. Requirement for permanent VP shunt insertion at 6 months' corrected age. (This is at the discretion of the treating team in the participating centre, according to routine clinical care).
- 5. Quality of life and health economic assessments:
 - a. Health-Related Quality of Life (HRQoL) in children: TNO-AZL Preschool Children's Quality of Life (TAPQOL) to be assessed at 12-months and 2 years' corrected age
 - b. HRQoL in primary caregiver: EuroQoL EQ-5D-5L to be assessed at baseline, 6 months, 12 months- and 2 years' corrected age

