6.1.1 Adverse Events

Adverse events include:

- an exacerbation (i.e., increase in the frequency or intensity) of a pre-existing illness, episodic event or symptom (initially recorded at the screening/baseline visit), that is detected after trial intervention
- occurrence of a new illness, episodic event or symptom, that is detected after trial intervention

Adverse events do NOT include:

- Medical or surgical procedures: the condition that leads to the procedure is the adverse event
- Pre-existing disease or a condition present before treatment that does not worsen
- Hospitalisation where no untoward or unintended response has occurred

Reporting of Adverse Events

The patient population includes preterm infants who are cared for on a neonatal intensive care for a prolonged period. Due to the nature of the patient population, a high incidence of adverse events can be foreseeable during their hospital stay. Only adverse events deemed as serious (see section 6.1.2) or as notifiable event (see section 6.2) will be recorded for the trial.

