6.2 Notifiable Adverse Events

The following adverse events should be reported within 5 working days using the Notifiable AE CRF:

- 1. New bleed identified on post-operative cranial ultrasound (CTCAE grade 2 and above)
- 2. Unexpected return to theatre for temporising device dysfunction, infection or CSF leak (CTCAE grade 3 and above). CSF infections will be monitored closely and reviewed at Trial Management Group meetings.
- 3. Return to theatre for insertion of an additional temporising device to treat loculated hydrocephalus (CTCAE grade 3 or above) or for a second endoscopic procedure to deloculate the ventricles
- 4. Confirmed or presumed infection associated with the trial procedure (grade 3 and above). This will include superficial (wound) and deep (CNS) infection. Confirmed infection will be where a micro-organism thought to be causative is isolated and presumed is when a micro-organism is not isolated, but the treating clinical team commences antibiotics. Of note, preterm infants may have many sources of infection and the **reporting here is confined to infection associated with the procedure (grade 3 and above).**
- 5. New development of seizures within 48 hours of the intervention (NEL) (grade 3 and above)
- 6. New development of focal neurological deficits within 48 hours of the intervention (NEL) (grade 3 and above)
- 7. Abandoned NEL procedure

Only non-serious AEs which constitute a notifiable event (listed above) should be reported to CCTU (via the trial database) within 5 working days.

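### The endoscopic limb of notifiable event 3 captures a first endoscopic deloculation after NEL but ordinarily not after a temporising device alone

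*Protocol*

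**What the plan says.** Item 3 of Protocol section 6.2 has two limbs. The first is "Return to theatre for insertion of an additional temporising device to treat loculated hydrocephalus (CTCAE grade 3 or above"; nothing in it refers to treatment arm. The second is "or for a second endoscopic procedure to deloculate the ventricles". It carries no CTCAE grade, and the word *second* is not defined.

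The arms differ in what happens at the index operation. Under section 4.2, Arm A infants "will undergo insertion of an endoscope into the lateral ventricle via a peel-away catheter on the side of higher blood load". Under section 4.3, Arm B infants "will undergo the standard surgical procedure to insert either a VAD or VSGS", with no endoscopy described.

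Section 6.1.1 fixes what enters the adverse-event data: "Only adverse events deemed as serious (see section 6.1.2) or as notifiable event (see section 6.2) will be recorded for the trial". Section 6.5 sends notifiable events to the Trial Management Group for review.

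In section 5.1.2, secondary outcome 4a is a count of adverse events that names returns to theatre among its contents. Outcome 4b counts further operations, including "addition of a second temporising device, surgery for loculated or isolated ventricles", without restriction by arm, technique or order. It has its own form: "We will have a separate CRF to record data related to these unexpected presentations and procedures".

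**The concern.** A safety event list should classify the same operation, done for the same reason, in the same way in both arms. Here the classification depends on how many endoscopic procedures the infant has already had, and that number is set by the randomised treatment: one in Arm A, none in Arm B.

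The list also decides which non-serious events exist in the adverse-event data at all. An arm-dependent item can therefore produce an apparent excess of endoscopic re-operations after NEL even if the true rates are equal. Safety is part of the trial's stated objective, and NEL is the treatment that the excess would count against.

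**Working it through.** The protocol states no figure on this point, so there is nothing to reproduce. The check compares each limb with each arm, then looks at the other routes by which the operation could be recorded.

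**Step 1. Status under item 3, reading the second limb literally.** The number of earlier endoscopic procedures comes from sections 4.2 (Arm A: 1) and 4.3 (Arm B: 0).

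| Event after the index operation | Arm A | Arm B |
|---|---|---|
| Additional temporising device for loculation, grade 3 or above (first limb) | notifiable | notifiable |
| First endoscopic deloculation, no additional device (second limb) | 1 + 1 = 2nd endoscopic procedure: notifiable | 0 + 1 = 1st endoscopic procedure: not notifiable under this limb |
| A further endoscopic deloculation (second limb) | notifiable | notifiable |

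Only the middle row differs by arm. The entry for Arm B assumes no earlier endoscopy. Section 10.2.2 leaves the clinician free to depart from the allocated treatment, so an exception is possible.

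**Step 2. Alternative readings of *second*, applied to a first endoscopic deloculation.**

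| Reading | Arm A | Arm B |
|---|---|---|
| Second endoscopic procedure of any kind (literal) | notifiable | not notifiable |
| Second deloculation | not notifiable | not notifiable |
| Any further operation after the index one | notifiable | notifiable |

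The second reading treats the arms alike but omits first deloculations that outcome 4b counts. Only the third treats the arms alike and includes the first deloculation, and the text does not say it.

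**Step 3. Was an NEL-only item intended?** Items 5, 6 and 7 of section 6.2 name NEL expressly. Item 3 does not, and its first limb covers both arms. The asymmetry looks like drafting rather than design.

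**Step 4. Other routes for an Arm B first deloculation.**

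- *Item 2 of section 6.2.* An unexpected return to theatre for device dysfunction, grade 3 and above, is notifiable in either arm. Table 6 includes insufficient drainage under dysfunction, so some Arm B returns may be notified this way.
- *Serious adverse events.* If the underlying condition is judged serious, it is reportable in either arm. Section 6.1.1 makes the condition, not the procedure, the adverse event. The report may therefore be filed as hydrocephalus, a foreseeable event in section 6.1.2.1, and not be recognisable as a deloculation.
- *Outcome 4b.* The operation is counted in both arms on a separate form.

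What remains exposed is a first endoscopic deloculation in Arm B that is not judged serious and not notified under item 2 or the first limb of item 3. It is missing from the notifiable events, and the recording rule in section 6.1.1 also keeps it out of the adverse-event count in 4a.

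**Step 5. Scale, for illustration only.** Let *p* be the share of infants in each arm who need endoscopic deloculation without an additional device. The protocol gives no value; 5% to 20% is assumed. With 50 infants per arm (section 8.1), expected notifications of first deloculations through the second limb are:

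- Arm A: 50 × 0.05 = 2.5 to 50 × 0.20 = 10
- Arm B: 0

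This describes one limb under one reading, before item 2 and deaths are considered. It is not an estimate of the bias in the whole notifiable-event stream.

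**The case against.** The strongest reply is that little is lost. The comparative record of re-operation is outcome 4b, which treats the arms alike and has its own form. Serious events reach the trials unit from both arms. The Independent Data Monitoring Committee has unrestricted access to unblinded data (section 8.3.3). No between-arm test or stopping rule is attached to item 3. The notifiable list is an alert list and need not match a complete count of operations. *Second* may simply have been meant as *further*.

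Most of this stands, and it limits the consequence. It does not remove the defect. Outcome 4b does not correct the notifiable-event data or the adverse-event count in 4a. Serious event reporting depends on a judgement of seriousness. In infants who are often still in hospital, the hospitalisation criterion is confined to stays beyond those expected under standard care (notes to Table 4). If *further* was meant, the text should say so, because sites can apply the present wording in different ways.

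A reader might infer that re-operation for loculated ventricles is notified in Arm A only, or that a control infant can never meet item 3. The document does not support either. The first limb applies to both arms, a control infant's later deloculation meets the second limb, and item 2 may capture some events. Nor does it support treating the illustrative counts in the working as an expected false signal, since the rate is assumed and only one limb is covered.

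**Conclusion.** The point holds in a narrow form. As worded, the second limb of item 3 makes notification of a first endoscopic deloculation depend on treatment arm: yes after NEL, ordinarily no after a temporising device alone. The direction is against NEL. The reach is limited to the notifiable-event stream, its review by the Trial Management Group and the count in outcome 4a. Outcome 4b and the primary outcome are unaffected.

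The size cannot be derived from the protocol. The conclusion rests on the literal reading of *second* and on Arm B infants having had no earlier endoscopy. The wording of the notifiable AE form is not available and could already resolve the ambiguity. This is a minor drafting correction, worth making because it removes a source of differential safety reporting.

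**What to change.** Replace the second limb of item 3 in section 6.2 with wording that applies on the same terms to both arms, for example: *or for any endoscopic deloculation of the ventricles carried out after the index operation*. Make the same change on the notifiable AE form, so that item 3 is consistent with the inclusion of "surgery for loculated or isolated ventricles" in outcome 4b.

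This changes a reporting definition only; it does not touch how any infant is treated. The cost is a few words in the protocol and on the form, and a few additional Arm B notifications.

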8.2.3 Allocation concealment mechanism and Blinding

This is a trial in which the primary outcome assessor, the Trial Statistician and the Clinical Project Manager will be blinded to the treatment allocation. The treating neurosurgeon and associated team cannot be blinded to treatment allocation due to nature of the study. Parents/legal guardians will be informed of the allocation after the procedure is completed. Parents will be informed by study team prior to the assessment that the assessor will be blinded to the treatment allocation, and they should therefore not divulge this information to the assessor inadvertently, which will be reinforced by the assessor before evaluation commences. All users of the Sealed Envelope system, with the exception of the Trial Statistician and the Clinical Project Manager, will be unblinded to treatment allocation via email and with the treatment allocated accessible through a secure portal, prior to the procedure being performed.

Given the study design, the treating neurosurgeon and associated research team cannot be blinded to treatment allocation. The increased operating time will also result in the Neonatal Intensive Care Unit (NICU) team being aware of the treatment arm. Previous Patient Advisory Group (PAG) work has identified that parents would like to be informed of the allocation and, failing to do so may result in many parents not taking part.

However, the primary outcome measure and other components of the Bayley IV developmental outcomes at 2 years' corrected age will be carried out by assessors blind to the treatment allocation.

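### Item 4 of section 6.2 makes attribution to the operation a condition for recording some infections, so those counts can differ by arm when true rates are equal

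*Protocol*

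**What the plan says.** Section 6.2 of the Protocol lists the notifiable adverse events. Item 4 covers infection, superficial or deep, that is linked to the trial procedure and is of grade 3 or above. It observes that "preterm infants may have many sources of infection" and then states that "reporting here is confined to infection associated with the procedure (grade 3 and above".

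Two categories are defined:
- Confirmed: "Confirmed infection will be where a micro-organism thought to be causative is isolated".
- Presumed: "presumed is when a micro-organism is not isolated, but the treating clinical team commences antibiotics".

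Item 4 gives no period after surgery, no wound, CSF or laboratory criterion for association, and does not name who judges it. Items 5 and 6 of the same list use a 48-hour window, and item 1 rests on an imaging finding.

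Section 6.1.1 limits what reaches the trial data: "Only adverse events deemed as serious (see section 6.1.2) or as notifiable event (see section 6.2) will be recorded for the trial".

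On blinding, section 8.2.3 says: "The treating neurosurgeon and associated team cannot be blinded to treatment allocation due to nature of the study". It adds: "The increased operating time will also result in the Neonatal Intensive Care Unit (NICU) team being aware of the treatment arm".

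Secondary outcome 4a (section 5.1.2) is the number of adverse events, among them "secondary bleeding in the brain, post-operative infections, temporising device survival, mortality, stroke, seizures". Infection is also the first risk in Table 6.

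**The concern.** Attribution is normally recorded about an event that is already in the data. Item 4 instead makes it the entry condition. In infants with many competing sources of infection, that opinion decides what is counted, and it is formed by people who know whether the infant had the longer endoscopic operation. The presumed category adds a second decision by the same staff, namely starting antibiotics.

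Safety is half of the trial's stated objective (section 1.2). If staff attribute infections more readily after one operation than after the other, the item 4 counts can show an excess that does not exist or hide one that does. The statistical analysis cannot repair this, because an event kept out of the trial data is not there to analyse. The concomitant-medication record would not help: it covers prophylactic antibiotics and anti-epileptic drugs only (sections 3.6 and 4.4).

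**Working it through.** **Step 1. Which infections depend on item 4 alone?**

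| Infection | Route into the trial data | Depends on attribution? |
|---|---|---|
| Serious, on the foreseeable list (e.g. sepsis) | SAE; within 5 working days if unrelated, 24 hours if related (6.1.2.1, 6.4.2.1) | Timing only |
| Serious, not on that list | SAE within 24 hours, related or not (Table 4, 6.1.2.2) | No |
| Unexpected return to theatre for infection, grade 3 or above | Item 2 of 6.2 | No association condition |
| Grade 3 or above, not classed as serious, no return to theatre | Item 4 only | Yes |
| Below grade 3, non-serious, no return to theatre | Not reported under item 4 in either arm | No |

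Only the fourth row is exposed. It need not be empty. These infants are long-stay inpatients, and the note to Table 4 restricts the hospitalisation criterion to admissions additional to, or longer than, those expected under standard care. An infection treated within the expected stay may therefore not be classed as serious.

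**Step 2. What can differential attribution do?**

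Inputs:
- n = 50 per arm (sections 3.3 and 8.1).
- r = true risk of an exposed infection, equal in both arms. Section 1.4 puts procedural risks, infection among them, below 5%, so 5% is used as a ceiling. 10% and 20% are assumptions that show the range.
- a = share of true infections judged associated with the procedure. The documents give no figure, so all shares are assumptions.

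Formulas: expected recorded count = n × r × a. With equal r, the recorded risk ratio is a(NEL) / a(control), whatever r is.

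| r | a, NEL / control | Expected counts | Difference | Ratio |
|---|---|---|---|---|
| 5% | 90% / 60% | 50×0.05×0.9 = 2.25; 50×0.05×0.6 = 1.50 | 0.75 | 1.5 |
| 5% | 60% / 90% | 1.50; 2.25 | −0.75 | 0.67 |
| 5% | 60% / 40% | 1.50; 1.00 | 0.50 | 1.5 |
| 5% | 75% / 25% | 1.875; 0.625 | 1.25 | 3.0 |
| 10% | 60% / 40% | 3.0; 2.0 | 1.0 | 1.5 |
| 20% | 60% / 40% | 6.0; 4.0 | 2.0 | 1.5 |
| 20% | 75% / 25% | 7.5; 2.5 | 5.0 | 3.0 |

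**Step 3. Could this produce a false significant result?**

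Exact binomial enumeration of the chance that Fisher's exact test gives p < 0.05, 50 per arm:

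| r | 50% / 50% | 60% / 40% | 75% / 25% |
|---|---|---|---|
| 5% | 0.09% | 0.15% | 0.59% |
| 10% | 0.7% | 1.4% | 6.0% |
| 20% | 1.8% | 4.5% | 24% |

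At the Protocol's own risk level the chance stays below 1%. The sample-size calculation in section 8.1 concerns the cognitive quotient and does not enter here.

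**The case against.** The strongest reply is that little is lost:
- Serious infections and returns to theatre are captured without the association condition.
- The grade 3 definition in section 6.4.1.2 largely overlaps the seriousness criteria, and the important-medical-condition criterion lets an investigator call a treated CSF infection serious.
- The wording is neutral between arms: item 4 refers to the trial procedure, which exists in both, and names wound and CNS infection. Association can be read as separating operative-site infection from the other infections of prematurity.
- Outcome 4a is a count for which section 8.3.7 names no formal test. The IDMC sees unblinded safety data, and the TMG reviews CSF infections.

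Most of this stands and narrows the point to the fourth row in Step 1. It does not remove it. Neutral wording does not make its application neutral when the person applying it knows the arm. The TMG and IDMC can review only what was reported, and neither is described as adjudicating infections blind to arm. For SAEs, section 6.4.2.2 says the site's causality opinion cannot be overruled.

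Three stronger readings are tempting but unsupported. A reader might infer that any infection attributed elsewhere is lost to the trial; the SAE and item 2 routes contradict that. A reader might infer a false excess with NEL of about 1.5; that ratio is only the quotient of two assumed shares, and reversing them gives 0.67. A reader might also infer a real risk of a spurious significant difference; at 5% the calculation shows otherwise.

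**Conclusion.** The point holds in a limited form. A wound, device or CSF/CNS infection of grade 3 or above that is neither reported as an SAE nor captured under item 2 enters the trial data only if judged associated with the procedure, with no time window. The item 4 counts can therefore differ by arm with equal true rates.

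Direction and size cannot be derived from the documents. With the shares tried at 5% risk, the distortion is 0.5 to 1.25 expected events between arms. Even that uses 5% for the exposed class alone, which is only part of all infection. The consequence lies in the descriptive safety comparison, where counts of one to three per arm are read by eye and one case gained or lost changes the impression.

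This rests on one inference: item 4 does not say who decides on association. That site staff decide follows from site reporting and the absence of any described blinded adjudication.

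**What to change.** Reword item 4 so that entry depends on anatomical site and time:

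1. Report every wound, device or subgaleal-pocket, or CSF/CNS infection of grade 3 or above (the existing threshold) that is culture-positive or treated with antibiotics.
2. Use one fixed number of days from trial surgery, chosen by the TMG and identical in both arms. It should not end at the next neurosurgical procedure. Section 1.1.1 reports fewer taps and revisions after lavage in the single-centre pilot, so such a window could run longer in the NEL arm.
3. Record association with the procedure as a separate field, not as an entry condition.
4. Report culture-positive CSF infection separately from presumed infection. The antibiotic-based category still depends on a decision by unblinded staff, and rewording cannot remove that.

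The cost is a rewording of one item, one extra field on the existing notifiable-event CRF and a few more reports. Systemic infections of prematurity remain outside item 4 because entry is by site. The change concerns recording only and affects no treatment decision. It acts prospectively, so it is worth making early.
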